## **Definition of Serious Adverse Event**

**A Serious Adverse Event is defined as any untoward medical occurrence that, meets at least 1 of the following serious criteria:**

### **Results in death (fatal)**

### **Immediately life-threatening**

The term “life-threatening” in the definition of “serious” refers to an event in which the subject was at risk of death at the time of the event. It does not refer to an event, which hypothetically might have caused death, if it were more severe.

### **Requires in-patient hospitalization or prolongation of existing hospitalization**

In general, hospitalization signifies that the subject has been detained (usually involving at least an overnight stay) at the hospital or emergency ward for observation and/or treatment that would not have been appropriate in the physician’s office or outpatient setting. Complications that occur during hospitalization are an adverse event. If a complication prolongs hospitalization or fulfills any other serious criteria, the event is serious. When in doubt as to whether “hospitalization” occurred or was necessary, the adverse event is to be considered serious. Hospitalization for elective treatment of a preexisting condition that did not worsen from baseline is not considered an adverse event.

### **Results in persistent or significant disability/incapacity**

The term disability means a substantial disruption of a person’s ability to conduct normal life functions. This definition is not intended to include experiences of relatively minor medical significance such as uncomplicated headache, nausea, vomiting, diarrhea, influenza, and accidental trauma (eg, sprained ankle) which may interfere with or prevent everyday life functions but do not constitute a substantial disruption.

### **Is a congenital anomaly/birth defect**

### **Other medically important serious event**

Medical or scientific judgment is to be exercised in deciding whether serious adverse event reporting is appropriate in other situations such as important medical events that may not be immediately life-threatening or result in death or hospitalization but may jeopardize the subject or may require medical or surgical intervention to prevent 1 of the other outcomes listed in the above definition. These events are typically to be considered serious.

Examples of such events include invasive or malignant cancers, intensive treatment in an emergency room or at home for allergic bronchospasm, blood dyscrasias or convulsions that do not result in hospitalization, or development of drug dependency or drug abuse.

## Recording Adverse Events and Serious Adverse Events

### Adverse Event and Serious Adverse Event Recording

- When an adverse event or serious adverse event occurs, it is the responsibility of the investigator to review all documentation (eg, hospital progress notes, laboratory, and diagnostics reports) related to the event.
- The investigator will then record all relevant adverse event/serious adverse event information in the Events case report form (CRF).
- The investigator must assign the following mandatory adverse event attributes:
  - Adverse event diagnosis or syndrome(s), if known (if not known, signs or symptoms);
  - Dates of onset and resolution (if resolved);
  - Did the event start prior to first dose of investigational product
  - Assessment of seriousness;
  - Severity (or toxicity defined below);
  - Assessment of relatedness to investigational product(s), other protocol-required therapies, and/or study-mandated activity and/or procedures, including [REDACTED] and F-FDG
  - Action taken; and
  - Outcome of event.
- If the severity of an adverse event worsens from the date of onset to the date of resolution, record a single event for each increased level of severity on the Event CRF.
- It is not acceptable for the investigator to send photocopies of the subject's medical records to sponsor/responsible contact research organization (CRO) in lieu of completion of the Events CRF page.
- If specifically requested, the investigator may need to provide additional follow-up information, such as discharge summaries, medical records, or extracts from the

medical records. In this case, all subject identifiers, with the exception of the subject number, will be blinded on the copies of the medical records before submission to Amgen.

- The investigator will attempt to establish a diagnosis of the event based on signs, symptoms, and/or other clinical information. In such cases, the diagnosis (not the individual signs/symptoms) will be documented as the adverse event/serious adverse event.

## **Evaluating Adverse Events and Serious Adverse Events**

### **Assessment of Severity**

The investigator will make an assessment of severity for each adverse event and serious adverse event reported during the study. The assessment of severity will be based on:

The Common Terminology Criteria for Adverse Events (CTCAE), version 5.0 which is available at the following location:

[http://ctep.cancer.gov/protocolDevelopment/electronic\\_applications/ctc.htm](http://ctep.cancer.gov/protocolDevelopment/electronic_applications/ctc.htm).

The adverse event grading scale to be used for this study will be the CTCAE and is described in Section 11.4. CRS, which will be graded using the criteria referenced in the publication by Lee et al (2014) (see Section 11.10) and TLS, which will be graded according to the Cairo Bishop criteria referenced in the publication by Coiffier et al (2008) (see Section 11.11), and ICANS will be using the criteria referenced in the publication by Lee et al (2019) (see Section 6.2.1.6.1.1).

### **Assessment of Causality**

- The investigator is obligated to assess the relationship between investigational product(s) protocol-required therapies, and/or study-mandated activity and/or procedure(s), including [REDACTED] F-FDG, and each occurrence of each adverse event/serious
- Relatedness means that there are facts or reasons to support a relationship between investigational product and the event.
- The investigator will use clinical judgment to determine the relationship.
- Alternative causes, such as underlying disease(s), concomitant therapy, and other risk factors, as well as the temporal relationship of the event to study treatment administration will be considered and investigated.
- The investigator will also consult the Investigator's Brochure and/or Product Information, for marketed products, in his/her assessment.
- For each adverse event/serious adverse event, the investigator must document in the medical notes that he/she has reviewed the adverse event/serious adverse event and has provided an assessment of causality.

- There may be situations in which a serious adverse event has occurred and the investigator has minimal information to include in the initial report. However, it is very important that the investigator always make an assessment of causality for every event before the initial transmission of the serious adverse event data.
- The investigator may change his/her opinion of causality in light of follow-up information and send a serious adverse event follow-up report with the updated causality assessment.
- The causality assessment is 1 of the criteria used when determining regulatory reporting requirements.

### **Follow-up of Adverse Event and Serious Adverse Event**

- The investigator is obligated to perform or arrange for the conduct of supplemental measurements and/or evaluations as medically indicated or as requested by Amgen to elucidate the nature and/or causality of the adverse event or serious adverse event as fully as possible. This may include additional laboratory tests or investigations, histopathological examinations, or consultation with other health care professionals.
- If a subject is permanently withdrawn from protocol-required therapies because of a serious adverse event, this information must be submitted to Amgen.
- If a subject dies during participation in the study or during a recognized follow-up period, the investigator will provide Amgen with a copy of any postmortem findings including histopathology.
- New or updated information will be recorded in the originally completed Events CRF.
- The investigator will submit any updated serious adverse event data to Amgen immediately and no later than 24 hours of receipt of the information.

### **Reporting of Serious Adverse Event**

#### **Serious Adverse Event Reporting via Paper CRF**

- Facsimile transmission of the Serious Adverse Event Report Form (see [Figure 11-1](#)) is the preferred method to transmit this information.
- In rare circumstances and in the absence of facsimile equipment, notification by telephone is acceptable with a copy of the Serious Adverse Event Report Form sent by overnight mail or courier service.
- Initial notification via telephone does not replace the need for the investigator to complete and sign the Serious Adverse Event Report Form within the designated reporting time frames.
- Once the study has ended, serious adverse event(s) suspected to be related to investigational product will be reported to Amgen if the investigator becomes aware of a serious adverse event. The investigator should use the paper-based Serious Adverse Event Report Form to report the event.

### Figure 11-1. Sample Serious Adverse Event Report Form (paper-based form)

**The following minimum fields must be completed prior to faxing the form:**  
1) Site Number; 2 ) Subject ID Number; 3) Serious Adverse Event Diagnosis; Serious Criteria Code; Start Date of Event; 10) Signature  
Ensure both pages are faxed with each submission.

**Note:** Only events that meet serious criteria (regardless of causal relationship to IP) should be reported on this form. Submit a Serious Adverse Event Report (SAER) form within 24 hours of the Investigator's knowledge of the event. \*Indicates a mandatory field.

Data on the AE Summary CRF (also known as Events CRF) must agree with data submitted on the SAER form in the following areas: adverse event term(s), serious criteria, and relationship of product to event.

Only include information that is relevant (pertinent) to the event(s) included on this SAER (eg, concomitant medications, medical history, laboratory and diagnostic tests)

#### Header Information

**New / Follow-up** – Indicate if this is a new adverse event, or a follow-up of a pre-reported event.

**Follow-up** – Send a follow-up report if additional data adds to or changes the clinical interpretation of the event. Some examples are:

- The initial reported event has changed and additional serious criteria have been met (such as if event outcome is now fatal).
- Signs and symptoms were reported at the time of the initial report and a final diagnosis has now been made.
- A change in relationship of a study procedure or activity has occurred from the initial report.
- A significant change has occurred in the start date of the event or start date of a suspect concomitant medication.
- Additional concomitant medications and/or diagnostics have been identified that may contribute to or explain the event.

When sending a follow-up report, either:

- On a photocopy of the prior report, add the additional information, re-sign and date, then fax in the follow-up form – or –
- Complete a new form with the new information. If the serious adverse event terms have not changed, please write, in section 3, the following: "No changes in serious adverse event terms from previous SAER form," then fax in the follow-up form.
- If a new serious adverse event term is to be added to the terms previously reported, add this new term to a photocopy of the initial form.
- If an earlier reported adverse event is being replaced by a new diagnosis or event term, on a photocopy of the initial report, strike through the term to be deleted, sign and date the deletion and add the updated event term.

#### 1. Site Information

**Site Number\*** – Enter your assigned site number for this study

**Investigator\*, Country\*, Date of Report, Reporter\*, Phone No., and Fax No.** – Enter information requested

#### 2. Subject Information

**Subject ID Number\*** – Enter the entire number assigned to the subject **Age at event onset, Sex, and Race** – Enter the subject's demographic information

**End of Study date** – If the subject has already completed the study or terminated the study early, enter the **End of Study date**

#### 3. Serious Adverse Event

Provide the date the Investigator became aware of this Serious Adverse Event Information

**Serious Adverse Event Diagnosis or Syndrome\*** –

- If the diagnosis is known, it should be entered. Do not list all signs/symptoms if they are included in the diagnosis.
- If a diagnosis is not known, the relevant signs/symptoms meeting serious criteria should be entered.
- If the event is fatal, the cause of death should be entered and autopsy results should be submitted, when available. Do not enter "Death," as this is an outcome, not an event.

**Date Started\*** – Enter date the adverse event first started rather than the date of diagnosis or hospitalization. For serious events, the start date is the date the event started, not the date on which the event met serious criteria. **This is a mandatory field.**

**Date Ended** – Enter date the adverse event ended. For serious events, this is not the date when the event no longer met serious criteria. If the event has not ended at the time of the initial report, a follow-up report should be completed when the end date is known. If the event is fatal/resulted in death, enter the date of death as the end date

If event occurred before the first dose of investigational product, add a check mark in the corresponding box.

**Serious Criteria Code\*** - This is a mandatory field for serious events – Enter reason why the reported event has met serious criteria:

- Immediately life-threatening – Use only if the subject was at immediate risk of death from the event as it occurred. Emergency treatment is often required to sustain life in this situation.
- If the investigator decides an event should be reported in an expedited manner, but it does not meet other serious criteria, "Other medically important serious event" may be the appropriate serious criterion.

**Relationship to IP\*** – The Investigator must determine and enter the relationship of the event to the IP at the time the event is initially reported. **This is a mandatory field.**

**Relationship to Amgen device\*** – The Investigator must determine and enter the relationship of the event to the Amgen device (eg, prefilled syringe, auto-injector) at the time the event is initially reported. **If the study involves an Amgen device, this is a mandatory field.** This question does not apply to non-Amgen devices used in the study (eg, heating pads, infusion pumps)

**Outcome of Event\*** – Enter the code for the outcome of the event at the time the form is completed. **This is a mandatory field.**

FORM-015482 Clinical Trial SAE Report – Phase 1-4 V 10.0 Effective date: 23-April-2018

SAER Created: 20-Jun-2022

Instruction Page 1 of 2

- Resolved – End date is known
- Not resolved/Unknown – End date is unknown
- Fatal – Event led to death

If event is related to a study procedure, such as a biopsy, radiotherapy or withdrawal of a current drug treatment during a wash-out period, add a check mark to the corresponding box. This does not include relationship to IP or concomitant medication administration – only diagnostic tests or activities mandated by the protocol.

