##### **6.2.1.4 Toxicity Management**

For the purpose of medical management, all adverse events and laboratory abnormalities that occur during the study must be evaluated by the investigator. The table of clinical toxicity grades from the NCI-CTCAE, Version 5.0 (available on CTEP home page: <http://ctep.info.nih.gov>) is to be used in the grading of adverse events and laboratory abnormalities that are reported as adverse events, each of which will be followed to satisfactory clinical resolution, except for CRS and NT which will be graded according to Lee et al (2019). AMG 340 has not been tested clinically in humans, so the adverse event profile in humans is not known.

Adverse events should be classified as pre-existing or as treatment-emergent adverse events:

- A treatment-emergent adverse event is defined as an adverse event not present prior to initiation of AMG 340 treatment, or an adverse event present prior to AMG 340 initiation that worsens in intensity and/or frequency after initiation of AMG 340 treatment.
- A pre-existing adverse event is an adverse event that does not meet these criteria. Subjects with pre-existing adverse events should be assessed for any underlying illness or other causes and treated as appropriate.

Subjects with treatment-emergent adverse events should also be assessed for intercurrent illness or other causes and treated as appropriate. If a treatment-emergent adverse event is unequivocally due to a subject's underlying malignancy or other extraneous cause, dosing with AMG 340 may be modified at the discretion of the Principal Investigator, following discussion with the Medical Monitors. If a treatment-emergent adverse event is not unequivocally due to the subject's underlying malignancy or other extraneous cause, regardless of whether there is a 'reasonable possibility' that the treatment-emergent adverse event is AMG 340-related, the dose of AMG 340 should be modified as follows:

- For subjects who have completed cycle 1 and have at least clinically or radiographically stable disease (SD, MR, PR or CR) but have experienced a reversible treatment-emergent adverse event, the dose of study drug can be delayed for up to 14 days after the scheduled dosing date. A subject for whom dosing is delayed > 14 days should be discontinued from the study.

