## **11.4 Appendix 4. Safety Events: Definitions and Procedures for Recording, Evaluating, Follow-up and Reporting**

### **Definition of Adverse Event**

Adverse Event Definition

• An adverse event is any untoward medical occurrence in a clinical study subject irrespective of a causal relationship with the study treatment.

• Note: An adverse event can therefore be any unfavorable and unintended sign (including an abnormal laboratory finding), symptom, or disease (new or exacerbated) temporally associated with the use of a treatment, combination product, medical device or procedure.

• Note: Treatment-emergent adverse events will be defined in the Statistical Analysis Plan (SAP).

Events Meeting the Adverse Event Definition

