5.1 Study Endpoints

5.1.1 Primary Endpoints Definitions

Treatment-Emergent Adverse Event (TEAE):

Events categorized as Adverse Events (AEs) starting on or after the first dose of AMG 340 as determined by “Did event start before first dose of AMG 340” equal to “No” or missing on the **Adverse Events** eCRF and up to and including 90 days after the last dose of AMG 340 (however, if subject start a new line of therapy before 90 days follow-up visit, safety follow-up will be performed through 30 days post last dose of AMG 340 or until subject begins a new line of therapy, whichever occurs later) excluding events reported after End of Study Date. **Events that are directly related to metastatic castrate-resistant prostate carcinoma cancer or disease progression (including, but not limited to, preferred terms “prostate cancer”, “progression of prostate cancer”, “prostate cancer metastatic”, “disease progression” etc.) will be excluded from TEAE analysis.**

Treatment-Related Adverse Event (TRAЕ):

A treatment-related AE is any treatment-emergent AE with the relationship flag on the **Adverse Events** eCRF indicating there is a reasonable possibility that the event may have been caused by AMG 340. In the unlikely event that the relationship is missing, the treatment-emergent event will be considered treatment-related and documented in a footnote of the treatment-related summary.

Dose-limiting Toxicities (DLTs):

Investigators determine whether a TEAE qualifies as a DLT per the definition described in protocol section 6.2.1.4.1. For an adverse event to qualify as DLT, the start date must be within 21 days from the date of first dose of AMG 340.

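### SAP 5.1.1 defines treatment-emergent events by onset alone, so an event recorded before the first dose that worsens on AMG 340 can drop out of the reported TEAE, TRAE and DLT tables

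*Protocol*

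**What the plan says.** Protocol 6.2.1.4 has two limbs for a treatment-emergent event. One is an event absent before AMG 340. The other is "an adverse event present prior to AMG 340 initiation that worsens in intensity and/or frequency after initiation of AMG 340 treatment". Protocol 2.2.4.3, which summarises 23 treated subjects, likewise counts events that occurred or worsened after the first dose.

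Protocol Appendix 4 (11.4) then hands the definition over: "Treatment-emergent adverse events will be defined in the Statistical Analysis Plan (SAP".

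SAP 5.1.1 has only the onset limb: "Events categorized as Adverse Events (AEs) starting on or after the first dose of AMG 340 as determined by" the eCRF item "Did event start before first dose of AMG 340", which must be No or missing. The other two event endpoints are built on it. For TRAEs: "A treatment-related AE is any treatment-emergent AE with the relationship flag on the" Adverse Events eCRF marked as related. For DLTs: "Investigators determine whether a TEAE qualifies as a DLT per the definition described in protocol section 6.2.1.4.1", with a start date no later than 21 days from the first dose.

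On recording, Appendix 4 tells the site, when severity worsens, to "record a single event for each increased level of severity on the Event CRF". The instructions for the paper serious-event form (Figure 11-1, item 3) add: "For serious events, the start date is the date the event started, not the date on which the event met serious criteria".

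**The concern.** TEAEs, TRAEs and DLTs are primary endpoints. The SAP narrows the first of them relative to the protocol, and the other two inherit the change. SAP Section 10, which lists departures from the protocol's analyses, names two other changes and not this one.

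Adverse events are collected from consent (Protocol 8.4.6.1.1) and screening may last up to 28 days (8.1.1), so events can be on record before dosing. If such an event becomes worse on treatment, the protocol calls it treatment-emergent, while the SAP's answer depends on how the site dates and flags it. The omission works in one direction only: it can remove events that the protocol definition includes. Final counts would also not be on the same basis as those in Protocol 2.2.4.3.

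**Working it through.** No figure in the documents tests this point, because the number of pre-dose events that later worsen is not given. The check is to take each way an event can be recorded and apply both definitions.

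| Event and how it is recorded | Protocol 6.2.1.4 | SAP 5.1.1 |
|---|---|---|
| First arises after dosing | Counts | Counts |
| Medical-history condition that flares after dosing, entered as a new AE (Appendix 4, events meeting the definition) | Counts | Counts |
| AE recorded between consent and first dose, grade rises; new record dated at worsening, pre-dose item No or missing | Counts | Counts |
| Same, but the new record carries the original onset and the pre-dose item is answered Yes | Counts | Does not count |
| AE recorded between consent and first dose, more frequent after dosing, same grade, no new record | Counts | Does not count |

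Rows 3 and 4 are the same clinical event. Appendix 4 makes onset date and the pre-dose question mandatory attributes of every event, but does not say whether a higher-severity record takes the date of worsening or the original onset. The documents therefore allow either row. Row 5 arises because the new-record rule is triggered by severity only, and the mandatory attributes include no frequency field.

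For DLTs, a row 4 event fails the SAP's first condition, since it is not a TEAE. Protocol 6.2.1.4.1 also builds a DLT on a treatment-emergent event, but in the protocol that term includes worsening. The reported DLT table could therefore differ from the DLTs that the Dose Level Review Team counted.

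Table 4-1 shows what one uncounted DLT would do to a tabulated result. The stated boundaries reproduce its cells. With 3 subjects, 0.236 × 3 = 0.708, so escalate at 0 DLTs, and 0.358 × 3 = 1.074, so de-escalate at 2. With 6 subjects, 0.236 × 6 = 1.416, so escalate at 1, and 0.358 × 6 = 2.148, so de-escalate at 3.

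| Subjects | True DLTs and action | Action with one DLT missing |
|---|---|---|
| 3 | 1: stay | Escalate |
| 3 | 2: de-escalate | Stay |
| 6 | 2: stay | Escalate |
| 6 | 3: de-escalate | Stay |

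This is sensitivity only. It does not show that a DLT would be lost.

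**The case against.** The strongest reply is that the recording rules already do most of the work. Each rise in severity becomes its own event with its own onset date, and the natural reading is the date of worsening. Protocol 6.2.1.6 takes the same approach for cytokine release syndrome. A pre-existing condition that becomes more frequent or more intense is an adverse event in its own right under Appendix 4. A missing pre-dose answer also counts as treatment-emergent. Most of this stands, and it limits the exposure to events recorded between consent and first dose. It does not remove the exposure, because a primary endpoint should not rest on a dating convention that is nowhere stated.

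It is also fair to say that Appendix 4 delegates the definition to the SAP and that Protocol 9.4.2.3.2 gives none, so silence in SAP Section 10 is weak evidence of an undeclared change. The two definitions still differ, and the reader of the final tables is not told.

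A reader might infer that Appendix 4 contains two conflicting start-date rules. It does not. The severity instruction splits records without dating them, and the serious-event form instruction concerns when an event became serious, not when its grade rose. The SAP flag comes from the Adverse Events eCRF, and start date is not among the fields that the form instructions say must agree between the two. Section 3 of the form does say its information must also be entered on a CRF, and Protocol 8.4.6.3 asks for consistency with the Events CRF. A site could therefore carry an original onset across, but nothing requires that for a higher-grade record.

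A reader might also take the laboratory limits in the eligibility criteria, or the grade 3 anemia and transaminase events in Protocol 2.2.4.3, as evidence of lost events. They are not. A baseline value inside the limits need not be an adverse event (Protocol 8.4.3), and 2.2.4.3 does not say that any of those events began before dosing.

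**Conclusion.** The concern holds in a limited form. SAP 5.1.1 omits the protocol's worsening limb, TRAEs and DLTs inherit the omission, and the recording instructions do not reliably make up for it. An adverse event recorded between consent and first dose that later worsens can be left out of the reported TEAE, TRAE and DLT tables. The clearest case is a rise in frequency without a change of grade.

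The number affected is unknown and probably small. That judgment assumes that few adverse events are recorded in a screening window of up to 28 days, and that most sites would date a higher-severity record at worsening.

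The documents do not support reading this as a threat to live dose escalation. The Dose Level Review Team decides on the protocol's DLT criteria and may consider events outside the window (Protocol 6.2.1.1 and 6.2.1.4.1), while the SAP's stated scope is the final analysis. Nor do they support saying that the SAP as written drops all worsened events.

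**What to change.** In SAP 5.1.1, add a second limb to the TEAE definition: or an AE present before the first dose that worsens on or after the first dose, within the same reporting window. Derive it by comparing post-dose records with the worst pre-dose grade of the same event. TRAEs and DLTs then follow without further change to their wording. If the onset-only rule is intended, SAP Section 10 should say so and give the reason.

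In the CRF completion instructions, state that:

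- each higher-severity record carries the date of worsening;
- the pre-dose item is answered for that record, not for the original event;
- a pre-dose AE that becomes more frequent after dosing is entered as a new AE record, consistent with Appendix 4. This has to be done at data entry, because the mandatory attributes include no frequency field from which to derive it.

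The first instruction also gives the 21-day DLT start-date condition an unambiguous date to work from.

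The cost is SAP wording, a CRF note and minor programming. Reported TEAE counts may rise slightly.
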